study drug dose, temporary cessation of study drug, or early termination of the trial. Any patient who receives at least one dose of study medication will be included in the evaluation for safety. Patients who do not receive at least one dose of study medication will be listed separately.

Compliance

Compliance to dosing will be measured via pill counts at each visit and by random medication callbacks. One callback will occur during the first 9 weeks of the study; and up to two more will occur during the remainder of the study.

Data Analysis

Power and Sample Size Considerations

Retention rate is one of the primary outcome measures and is a proportion. Many of the descriptions of the patients= use as determined by opiate positive urines may also be a proportion (e.g., percentage of subjects who have 6 consecutive clean urines). The maximum variability for a proportion occurs when the proportion equals one-half, thus any sample size estimate obtained for this proportion would be conservative in that it will require more subjects than actually needed. To compute a 95% confidence interval for the observed proportion, with precision of $\pm 5\%$, a sample size of approximately 400 is needed when the expected proportion is 0.5.

Since the dropout rate is expected to be between 70 and 80%, the total number of patients that need to be enrolled is between 500 and 575. This number has been rounded to 600 to permit each of the primary VA Medical Centers (across 6 states) to enroll about 100 subjects. Each site physician will be allowed to enroll between 10 and 20 subjects so that they gain sufficient experience to permit results to be generalized.

Demography and Baseline Outcome Analyses

The number of patients enrolled in the study will be summarized overall, by site and by treatment setting. For patients who are screened but not enrolled, a distribution of the reasons for discontinuation will be provided.

Demographic, as well as other pretreatment characteristics and baseline parameters, will be summarized overall, by site and by treatment setting.

Efficacy Analyses

Although the study design does not permit an unconfounded assessment of treatment efficacy, treatment improvement, or lack thereof, will be documented.

Patient retention rates will be the primary outcome measure and will be summarized using descriptive statistics, overall, by site and by treatment setting. The NIDA-VACSP Multicenter Buprenorphine

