Study #999A, a 16-week efficacy and safety study using a traditional clinical trial setting, has shown a retention rate of 51%. About 82% of those completers, chose to enter the #999 Extension Study which provided for an additional 36 weeks of maintenance. Of the patients entering the extension study, 57% completed a total of 52 weeks (this would be a 24% retention rate for all patients enrolled). In the NIDA-VACSP Multicenter Buprenorphine Studies #1008A and B, a retention rate of about 30% was seen for 52 weeks for all patients enrolled.

The proposed length of patient accrual for this study is estimated to be 20 weeks. This is based upon the assumption that 5 patients will be able to be recruited in each state per week. A patient=s participation in the study can last up to 1 year with follow-up being conducted thirty days after their completion/termination in the study. Accounting for the needs for data edits and clarifications, the total length of the study at each site is estimated to be 2 years.

Emphasis also will be placed on the urine toxicology screen results, the self-reports of drug use and the clinician rating of improvement obtained at the end of treatment. Other self-reports and ratings will be considered secondary. The results (actual values and change from baseline) will be summarized using descriptive statistics overall, by site and by treatment setting. These summaries will be performed for the end of treatment, and for the follow-up separately.

The effects of the medication itself, as well as, the effects of withdrawal from opiates will be measured. The results will be summarized using descriptive statistics overall, by site and by treatment setting.

The Office Visit Checklist (Form 09) contains information on the treatment prescribed (induction, maintenance, dose taper) and on the actual prescription (amount, frequency, duration). The information from this checklist will be summarized using descriptive statistics. At a minimum, the summaries will be prepared overall, by site and by treatment setting. Further summaries by induction, maintenance and/or dose-tapering may be performed.

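### The enrolment target divides 400 by the expected dropout rate as if it were the retention rate; 600 patients are still enough for retention, but not for a ±5% claim on patients present at 52 weeks

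*Protocol*

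**What the plan says.** The Protocol, under Data Analysis, Power and Sample Size Considerations, introduces the calculation for the retention rate and adds that many descriptions of urine results may also be proportions. The target is a 95% interval with a half-width of 5 percentage points, for which "a sample size of approximately 400 is needed when the expected proportion is 0.5".

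The next paragraph turns this into an enrolment figure: "Since the dropout rate is expected to be between 70 and 80%, the total number of patients that need to be enrolled" is put at 500 to 575. That is rounded to 600, so that each of six states enrols about 100.

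Under Efficacy Analyses, retention is named as the primary outcome measure. The same section reports retention in the sponsor's earlier buprenorphine studies. In one programme, 51% completed 16 weeks, about 82% of those entered an extension, and 57% of those reached 52 weeks: "this would be a 24% retention rate for all patients enrolled". In two other studies, "a retention rate of about 30% was seen for 52 weeks for all patients enrolled".

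**The concern.** An allowance for dropout normally divides the number needed by the fraction expected to remain. With 70–80% dropout that fraction is 0.20–0.30, and the enrolment figure should be several times 400. The Protocol's figure is only 25% to 44% above 400, which is the allowance for 20–30% dropout.

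The step is also out of place for the outcome that opens the section. Leaving the study is the event that retention counts, so a patient who drops out is a known failure and not a missing observation. An allowance for dropout makes sense only for a proportion calculated among patients who remain.

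At stake is the stated justification for 600 patients. As written, it leads a reader to expect at least 400 patients in any end-of-study proportion. At the stated dropout, an end-of-study urine or rating summary restricted to patients still present would have far fewer.

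**Working it through.** **Inputs.** From Power and Sample Size Considerations: 95% confidence, half-width 0.05, p = 0.5, base size about 400, dropout 70–80%, enrolment 500 to 575, rounded to 600. From Efficacy Analyses: 51%, 82% and 57% for the first programme, and about 30% at 52 weeks for the other two studies.

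**1. Base size.** n = z²p(1−p)/d² = 1.96² × 0.25 / 0.05² = 384. With z = 2 it is exactly 400. The Protocol's approximate 400 is sound.

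**2. Reproducing 500 to 575.**
- 400/0.80 = 500 and 400/0.70 = 571. This matches the stated range, with 571 rounded up to 575.
- Standard inflation N/(1−d) with d = 0.70 and 0.80: 400/0.30 = 1,334 (rounded up) and 400/0.20 = 2,000. No match.
- Additive inflation N(1+d): 400 × 1.70 = 680 and 400 × 1.80 = 720. No match.

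Of these routes, only division by the stated dropout rate gives the stated range.

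**3. Is 70–80% really dropout?** The first programme gives 0.51 × 0.82 × 0.57 = 0.238, or 24% retained and 76% lost at 52 weeks. The other two studies retained about 30%, so about 70% were lost. Both losses lie within 70–80%. The word used in the text is right and the division is wrong.

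**4. What 600 leaves after that dropout.** 600 × 0.20 = 120 and 600 × 0.30 = 180. Keeping 400 of 600 would require dropout of at most 1 − 400/600 = 33.3%.

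**5. Precision.** Half-width = 1.96 × √(p(1−p)/n), simple binomial:

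| Denominator | n | p | Half-width (points) |
|---|---|---|---|
| Present at 52 weeks, 80% dropout | 120 | 0.50 | ±8.9 |
| Present at 52 weeks, 70% dropout | 180 | 0.50 | ±7.3 |
| Protocol's target | 400 | 0.50 | ±4.9 |
| All enrolled | 600 | 0.50 | ±4.0 |
| All enrolled, earlier retention | 600 | 0.30 | ±3.7 |
| All enrolled, earlier retention | 600 | 0.24 | ±3.4 |

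**The case against.** The strongest reply is that the slip does no harm to the primary outcome. The calculation is introduced for retention, all 600 enrolled patients count towards it, and its precision is better than promised. The study is open-label, single-arm and descriptive, and no test or decision threshold depends on the derivation. This stands. It limits the consequence, but it does not make the derivation correct.

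Three stronger readings are tempting, and the document does not support them.

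- A reader might infer that 600 patients cannot support ±5% at all, or that 1,334 to 2,000 must be enrolled. The Protocol never says that the 400 are completers, and both earlier 52-week retention figures are expressed for everyone enrolled. The larger numbers show only what the sentence's own logic would require.
- A reader might infer that every urine proportion falls short. Urine is collected weekly for the first nine weeks, when more patients should be present than at 52 weeks. If the earlier 51% at 16 weeks applied here, 600 × 0.51 = 306 would remain, giving ±5.6 points at p = 0.5. A measure such as a run of six opiate-free samples can also be scored on all enrolled patients.
- A reader might infer that the plan intends to calculate retention among completers. No section says so.

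It could also be argued that dropout was simply written where retention was meant. The arithmetic would then follow, but an expected retention of 70–80% would conflict with the 24% and about 30% reported under Efficacy Analyses. The sentence needs correcting on either reading.

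One further reservation stands. Patients who detoxify successfully finish at 9 to 12 weeks (Patient Assignment and Length of Study), so 120 to 180 is the number remaining only if the stated rate applies to the mixed detoxification and maintenance population. The Protocol does not settle this.

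**Conclusion.** The derivation of 500 to 575 is wrong as written: it divides by the expected dropout rate. The planned 600 is nevertheless adequate for retention, where no inflation was needed. It gives about ±4.0 points at p = 0.5 and ±3.4 to ±3.7 at the 24–30% seen before.

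The ±5% claim fails for proportions restricted to patients still in the study at 52 weeks: about 120 to 180 patients and ±7.3 to ±8.9 points at p = 0.5. This assumes that the 70–80% applies to everyone enrolled.

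All half-widths are simple binomial. Patients are grouped under site physicians who enrol 10 to 20 each, and the Protocol gives no intraclass correlation, so the true intervals may be wider.

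**What to change.** In Power and Sample Size Considerations:

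1. Keep the total at 600, and delete the dropout sentence with its 500-to-575 range. The existing reason of about 100 patients in each of six states can stay, as can the accrual plan (5 per week × 6 states × 20 weeks = 600).
2. State that the precision claim applies to proportions with all enrolled patients as denominator: about ±4.0 points at p = 0.5 and ±3.4 to ±3.7 at 24–30%, simple binomial, before any clustering by site physician.
3. Add that a proportion restricted to patients still in the study at 52 weeks would rest on about 120 to 180 patients at the expected dropout, with ±7.3 to ±8.9 points at p = 0.5, and so does not meet ±5%.

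This does not require all urine proportions to use all enrolled patients. That would need a rule for samples missing after dropout, which a protocol commonly leaves to the statistical analysis plan.

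The cost is a few sentences and no extra patients. The stated precision for end-of-study proportions among patients present becomes less favourable.

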Appendix I ADVERSE EVENTS

Definitions:

Adverse Event (or Adverse Experience)

Any untoward medical occurrence in a patient or clinical investigation subject administered a pharmaceutical product and which does not necessarily have to have a causal relationship with this treatment. An adverse event (AE) can therefore be any unfavorable and unintended sign (including an abnormal laboratory finding, for example), symptom, or disease temporally associated with the use of a medicinal product, whether or not considered related to the medicinal product.

Adverse Drug Reaction (ADR)

In the *pre-approval clinical experience* with a new medicinal product or its new usages, particularly as the therapeutic dose(s) may not be established, *all noxious and unintended responses to a medicinal product related to any dose should be considered adverse drug reactions*. (The phrase "responses to a medicinal products" means that a causal relationship between a medicinal product and an adverse event is at least a reasonable possibility, i.e., the relationship cannot be ruled out.)

The term "severe" is often used to describe the intensity (severity) of a specific event (as in mild, moderate, or severe myocardial infarction); the event itself, however, may be of relatively minor medical significance (such as severe headache). This is *not* the same as "serious," which is based on patient/event *outcome or action* criteria usually associated with events that pose a threat to a patient's life or functioning. Seriousness (not severity) serves as a guide for defining regulatory reporting obligations.

A serious adverse event (experience) or reaction is any untoward medical occurrence that at any dose:

Results in death.

Is life-threatening, (NOTE: The term "life-threatening" in the definition of "serious" refers to an event in which the patient was at risk of death at the time of the event; it does not refer to an event which hypothetically might have caused death if it were more severe.)

Requires inpatient hospitalization or prolongation of existing hospitalization,

Appendix I ADVERSE EVENTS

Results in persistent or significant disability/incapacity, or Is a congenital anomaly/birth defect. Medical and scientific judgment should be exercised in deciding whether expedited reporting is appropriate in other situations, such as important medical events that may not be immediately life-threatening or result in death or hospitalization but may jeopardize the patient or may require intervention to prevent one of the other outcomes listed in the definition above. These should also usually be considered serious.

Expectedness of an Adverse Drug Reaction

An "unexpected" adverse reaction is one, the nature or severity of which is not consistent with information in the relevant source documents (e.g.,Investigator's Brochure, Buprenex labeling). Until source documents are amended, expedited reporting is required for additional occurrences of the reaction.

Causality assessment is required for clinical investigation cases. All cases judged by either the reporting health care professional or the sponsor as having a reasonable suspected causal relationshipto the medicinal product qualify as ADRs.

Note: The expression "reasonable causal relationship" is meant to convey in general that there are facts (evidence) or arguments to suggest a causal relationship.

REPORTING TIME FRAMES

Fatal or Life-Threatening Unexpected ADRs (Expedited Reporting)

Certain ADRs may be sufficiently alarming so as to require very rapid notification to regulators in countries where the medicinal product or indication, formulation, or population for the medicinal product are still not approved for marketing, because such reports may lead to consideration of suspension of, or other limitations to, a clinical investigation program. Fatal or life-threatening, unexpected ADRs occurring in clinical investigations qualify for very rapid reporting.

Appendix I

ADVERSE EVENTS

The sponsor should be notified (e.g., by telephone, facsimile transmission, or in writing) as soon as possible but no later than 24 hours after first knowledge by the investigator that a case qualifies, followed by as complete a report as possible within 5 additional calendar days. This report should include an assessment of the importance and implication of the findings, including relevant previous experience with the same or similar medicinal products.

All Other Serious, Unexpected ADRs

Serious, unexpected reactions (ADRs) that are not fatal or life-threatening must be communicated to the sponsor as soon as possible but no later than 5 calendar days after first knowledge by the investigator that the case meets the minimum criteria for expedited reporting.

Minimum Criteria for Reporting

Information for final description and evaluation of a case report may not be available within the required time frames for reporting outlined above. Nevertheless, for regulatory purposes, initial reports should be submitted within the prescribed time as long as the following minimum criteria are met: an identifiable patient; a suspect medicinal product; an identifiable reporting source; and an event or outcome that can be identified as serious and unexpected, and for which, in clinical investigation cases, there is a reasonable suspected causal relationship. Follow-up information should be actively sought and submitted as it becomes available.

How to Report

The MedWatch form has been a widely accepted standard for expedited adverse event reporting. All reports must be sent to the sponsor.

Post-Study Events

Serious adverse events that occurred after the patient had completed the clinical study (i.e. during follow-up) should be reported by an investigator to the sponsor. Such cases should be regarded for expedited reporting purposes as though they were study reports. Therefore, a causality assessment and determination of expectedness are needed for a decision on whether or not expedited reporting is required.

The following list of items has its foundation in several established precedents from various regulatory authority forms and guidelines. Some items may not be relevant depending on the circumstances. The minimum information required for expedited reporting purposes is: an identifiable patient, the name of a suspect medicinal product, an identifiable reporting source, and an event or outcome that can be identified as serious and unexpected and for which, in clinical investigation cases, there is a reasonable suspected causal relationship. Attempts should be made to obtain follow-up information on as many other listed items pertinent to the case.

1. Patient Details: Initials, Other relevant identifier (clinical investigation number, for example), Gender, Age and/or date of birth, Weight, Height.

Appendix II

KEY DATA ELEMENTS FOR INCLUSION IN EXPEDITED REPORTS OF SERIOUS ADVERSE DRUG REACTIONS

- 2. **Suspected Medicinal Product(s)**: Brand name as reported, International Non-Proprietary Name (INN), Batch number, Indication(s) for which suspect medicinal product was prescribed or tested, Dosage form and strength, Daily dose and regimen (specify units e.g., mg, mL, mg/kg), Route of administration, Starting date and time of day, Stopping date and time, or duration of treatment.
- **3. Other Treatment(s):** For concomitant medicinal products (including non-prescription/OTC medicinal products) and non-medicinal product therapies, provide the same information as for the suspected product.
- **4. Details of Suspected Adverse Drug Reaction(s)**: Full description of reaction(s) including body site and severity, as well as the criterion (or criteria) for regarding the report as serious should be given. In addition to a description of the reported signs and symptoms, whenever possible, attempts should be made to establish a specific diagnosis for the reaction. Start date (and time) of onset of reaction, Stop date (and time) or duration of reaction, Dechallenge and rechallenge information, Setting (e.g., hospital, out-patient clinic, home, nursing home), Outcome: Information on recovery and any sequelae; what specific tests and/or treatment may have been required and their results; for a fatal outcome, cause of death and a comment on its possible relationship to the suspected reaction should be provided. Any autopsy or other post-mortem findings (including a coroner's report) should also be provided when available. Other information: anything relevant to facilitate assessment of the case, such as medical history including allergy, drug or alcohol abuse; family history; findings from special investigations.
- **5. Details on Reporter of Event (Suspected ADR):** Name, Address, Telephone number, Profession (speciality).
- **6.** Administrative and Sponsor/Company Details: Source of report: Was it spontaneous, from a clinical investigation (provide details), from the literature (provide copy), other? Date event report was first received by sponsor/manufacturer, Country in which event occurred, Type of report filed to authorities: initial or follow-up (first, second, etc.), Name and address of sponsor/manufacturer/company, Name, address, telephone number, and FAX number of contact person in reporting company or institution, Identifying regulatory code or number for marketing

Appendix II

KEY DATA ELEMENTS FOR INCLUSION IN EXPEDITED REPORTS OF SERIOUS ADVERSE DRUG REACTIONS

authorization dossier or clinical investigation process for the suspected product (for example IND or CTX number, NDA number), Sponsor/manufacturer's identification number for the case (This number should be the same for the initial and follow-up reports on the same case).
